6.8 Interstitial lung disease (ILD)/Pneumonitis

General Guidance for Interstitial lung disease (ILD)/Pneumonitis events

Interstitial lung disease (ILD) / pneumonitis has been identified as an adverse drug reaction for abemaciclib. Adverse events reported included events such as interstitial lung disease, pneumonitis, obliterative bronchiolitis, organizing pneumonia, pulmonary fibrosis. The majority of events were Grade 1 or Grade 2 with serious cases and fatal events reported.

Monitor for clinical symptoms or radiological changes indicative of ILD/pneumonitis and please ask patients to report any new or worsening pulmonary symptoms. Symptoms may include hypoxia, cough, dyspnea, or interstitial infiltrates on radiologic exams.; these symptoms should be investigated and treated as per local clinical practice and/or guidelines (including corticosteroids as appropriate). Infectious, neoplastic, and other causes for such symptoms should be excluded by means of appropriate investigations. Investigations may include imaging such as high resolution computer tomography (HRCT), bronchoalveolar lavage (BAL), and biopsy as clinically indicated (see also Table 13: *refer to dose adjustment table for interstitial lung disease/pneumonitis*).

Table 13: Dose Modification and Management — Interstitial Lung Disease/Pneumonitis

Toxicity	Arm 1 – abemaciclib alone	Arm 2 – Abemaciclib plus MK-6482
Grade 1 or 2	No dose modification is required.	No dose modification is required.
Persistent or recurrent Grade 2 toxicity that does not resolve with maximal supportive measures within 7 days to baseline or Grade 1	Suspend dose until toxicity resolves to baseline or Grade 1. Resume at next lower dose.	Hold abemaciclib and MK-6482 until resolution of toxicity to baseline or grade 1. Resume abemaciclib at lower dose level. Resume MK-6482 at lower dose level.
Grade 3 or 4	Discontinue abemaciclib.	Discontinue abemaciclib and MK-6482.

7. ADVERSE EVENTS: LIST AND REPORTING REQUIREMENTS

Adverse event (AE) monitoring and reporting is a routine part of every clinical trial. The following list of reported and/or potential AEs (Section 7.1) and the characteristics of an observed AE (Section 7.2) will determine whether the event requires expedited reporting **in addition** to routine reporting.

7.1 Expected Toxicities

7.1.1 Adverse events list for abemaciclib

Frequent adverse events reported in >20% of patients treated with abemaciclib single-agent include diarrhea (90%), fatigue (65%), nausea (64%), decreased appetite (46%), abdominal pain (39%), vomiting (35%), headaches (21%), creatinine increased (99%), white blood cell decreased (91%), neutrophil count decreased (88%), anemia (69%), platelet count decreased (41%), ALT increased (30%), AST increased (26%), hypokalemia (26%), hyponatremia (21%).

Grade 3 adverse events reported in >5% of patients treated with abemaciclib single-agent include diarrhea (20%), fatigue (13%), white blood cell decreased (28%), neutrophil count decreased (27%), hypokalemia (5%).

7.1.2 Adverse events list for MK-6482

Based on preliminary phase I data, frequent adverse events with MK-6482 include anemia (75%), fatigue (67%), dyspnea (47%), nausea (33%), and cough (31%).

The only frequent grade 3 adverse event reported in > 10% of patients treated with MK-6482 single-agent is anemia (13%).

7.2 Adverse Event Characteristics

7.2.1 Adverse event

An AE is any unfavorable and unintended sign, symptom, or disease associated with the use of an investigational product or other protocol-imposed intervention, regardless of attribution. Those include:

- AEs not previously observed that emerge during the protocol-specified AE reporting period.
- Complications that occur as a result of protocol-mandated interventions (e.g., invasive procedures such as cardiac catheterizations)
- If applicable, AEs that occur prior to assignment of study treatment associated with medication washout, treatment run-in, or other protocol-mandated intervention

- Pre-existing medical conditions other than the condition being studied, being judged by the investigator to have worsened in severity or frequency or changed in character during the protocol-specified AE reporting period

7.2.2 CTCAE term (AE description) and grade.

The descriptions and grading scales found in the revised NCI Common Terminology Criteria for Adverse Events (CTCAE) version 5.0 will be utilized for AE reporting. All appropriate treatment areas should have access to a copy of the CTCAE version 5.0. A copy of the CTCAE version 5.0 can be downloaded from the CTEP web site http://ctep.cancer.gov/protocolDevelopment/electronic_applications/ctc.htm.

7.2.3 Attribution of the AE.

Definite – The AE *is clearly related* to the study treatment.

Probable – The AE *is likely related* to the study treatment.

Possible – The AE *may be related* to the study treatment.

Unlikely – The AE *is doubtfully related* to the study treatment.

Unrelated – The AE *is clearly NOT related* to the study treatment.

Attributing the AE to the study treatments (s) means that there is a plausible temporal relationship between the onset of the AE and administration of the study drugs, and the AE cannot be readily explained by the patient's clinical state, intercurrent illness, or concomitant therapies; and/or the AE follows a known pattern of response to the study drug(s); and/or the AE abates or resolves upon discontinuation of the study drug(s) or dose reduction and, if applicable, reappears upon re-challenge.

7.2.4 Serious adverse event

An AE should be classified as an SAE if the following criteria are met:

- It results in death
- It is life threatening. It does not include an AE that, had it occurred in a more severe form, might have caused death.
- It requires or prolongs inpatient hospitalization
- It results in persistent or significant disability/incapacity
- It results in a congenital anomaly/birth defect in a neonate/infant born to a mother exposed to the investigational drug
- It is considered a significant medical event by the investigator based on medical judgment, notably by jeopardizing the patient or leading to require medical/surgical intervention to prevent one of the outcomes listed above.

7.2.5 Diagnosis, signs and symptoms

If known at the time of reporting, a diagnosis should be reported rather than individual signs and symptoms (e.g., record only liver failure or hepatitis rather than jaundice, asterixis, and elevated transaminases). However, if a constellation of signs and/or symptoms cannot be medically characterized as a single diagnosis or syndrome at the time of reporting, it is acceptable to report the information that is currently available. If a diagnosis is subsequently established, it should be reported as follow-up information.

7.2.6 Death

All deaths that occur during the protocol-specified AE reporting period, regardless of attribution, will be reported to the appropriate parties. When recording a death, the event or condition that caused or contributed to the fatal outcome should be reported as the single medical concept. If the cause of death is unknown and cannot be ascertained at the time of reporting, report “Unexplained Death.”

7.2.7 Pre-existing condition

A pre-existing medical condition is one that is present at the start of the study. Such condition should be reported as medical and surgical history. A pre-existing medical condition should be reassessed throughout the trial and reported as an AE or SAE only if the frequency, severity, or character of the condition worsens during the study. When reporting such events, it is important to convey the concept that the pre existing condition has changed by including applicable descriptors

7.2.8 Hospitalizations

Any AE that results in hospitalization or prolonged hospitalization should be documented and reported as an SAE. If a patient is hospitalized to undergo a medical or surgical procedure as a result of an AE, the event responsible for the procedure, not the procedure itself, should be reported as the SAE. For example, if a patient is hospitalized to undergo coronary bypass surgery, record the heart condition that necessitated the bypass as the SAE.

Hospitalizations for the following reasons do not require reporting:

- Hospitalization or prolonged hospitalization for diagnostic or elective surgical procedures for pre-existing conditions
- Hospitalization or prolonged hospitalization required to allow efficacy measurement for the study
- Hospitalization or prolonged hospitalization for scheduled therapy of the target disease of the study

7.2.9 Pregnancy

If a female subject becomes pregnant while on study, she will be taken off study treatment. Pregnancy occurring on study or within 3 months after the last study drug should be reported

expeditiously to the sponsor. Follow-up to obtain the outcome of the pregnancy should also occur. Abortion, whether accidental, therapeutic, or spontaneous, should always be classified as serious, and expeditiously reported as an SAE. Similarly, any congenital anomaly/birth defect in a child born to a female subject exposed to the study drugs should be reported as an SAE.

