3.1.8 Women of child-bearing potential and men must agree to use adequate contraception (intrauterine device or barrier method of birth control; abstinence) prior to study entry, for the duration of study participation and 6 months after completion abemaciclib plus MK-6482 and at least 3 weeks after the completion of abemaciclib administration. If condoms are used as a barrier method, a spermicidal agent should be added as a double barrier protection. A negative pregnancy serum test should be obtained within 7 days of therapy initiation. Should a woman become pregnant or suspect she is pregnant while she or her partner is participating in this study, she must discontinue treatment immediately. Data on fetal outcome and breast-feeding are to be collected for regulatory reporting and drug safety evaluation.. Men treated or enrolled on this protocol must also agree to use adequate contraception prior to the study, for the duration of study participation, and 6 months after completion abemaciclib plus MK-6482 and at least 3 weeks after the completion of abemaciclib administration.

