5.7 Duration of Follow Up

After removal from protocol therapy, participants will be followed for safety for 90 days, or until initiation of new cancer-directed treatment, or until death, whichever occurs first.

Participants removed from protocol therapy with ongoing treatment-related adverse event(s) will be followed until resolution or stabilization of the adverse event(s), initiation of new cancer-directed treatment, or death.

Participants removed from protocol who did not experience disease progression will be followed as per protocol until progression, initiation of new cancer-directed treatment, or death.

Participants will be followed for survival and next line of systemic treatments every 6 months, until death or 2 years after treatment discontinuation. Follow-up will be performed by phone calls and review of health records.

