7.2.10 Post-Study Adverse Events

The investigator should expeditiously report any SAE occurring after a patient has completed or discontinued study participation if attributed to prior study drugs exposure. If the investigator should become aware of the development of cancer or a congenital anomaly in a subsequently conceived offspring of a female patient who participated in the study, this should be reported as an SAE.

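### Pregnancy reporting ends 3 months after the last dose but contraception after the combination runs 6 months, so an arm 2 pregnancy starting in months 3 to 6 is not clearly reportable as such

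*Combined protocol and SAP*

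**What the plan says.** **Reporting rule.** Section 7.2.9 states: "Pregnancy occurring on study or within 3 months after the last study drug should be reported", and the sentence goes on to require that this be done quickly and to the sponsor. The next sentence asks for follow-up to learn the outcome of the pregnancy. Neither sentence distinguishes the arms.

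**Contraception rule.** Section 3.1.8 binds women of child-bearing potential and men "for the duration of study participation and 6 months after completion abemaciclib plus MK-6482", and for at least 3 weeks after abemaciclib. The same item says: "Data on fetal outcome and breast-feeding are to be collected for regulatory reporting and drug safety evaluation".

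**Provisions without an end date.**
- Section 7.2.9: "Abortion, whether accidental, therapeutic, or spontaneous, should always be classified as serious, and expeditiously reported as an SAE". A birth defect in the child of an exposed female subject is likewise an SAE.
- Section 7.2.10 requires reporting of "any SAE occurring after a patient has completed or discontinued study participation if attributed to prior study drugs exposure". It also covers "development of cancer or a congenital anomaly in a subsequently conceived offspring of a female patient who participated in the study", if the investigator becomes aware of it.
- Section 7.3.4 requires SAEs judged related to the Merck product to be reported whenever they come to light, including after its standard window has closed.

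**Follow-up.** Under section 5.7, after therapy stops, "participants will be followed for safety for 90 days", or until new cancer treatment or death if sooner. Contact for survival and next-line therapy continues every 6 months for up to 2 years. Section 5.8 lists only three reasons for leaving the study: loss to follow-up, withdrawal of consent for data submission, and death.

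**The concern.** Section 3.1.8 sets a period after the combination in which pregnancy is to be avoided, and asks for fetal-outcome data for regulatory and safety purposes. The operative reporting sentence in 7.2.9 stops halfway through that period for arm 2. An investigator who follows 7.2.9 literally could learn of a pregnancy that began in month 4 after the last combination dose and conclude that it need not be sent to the sponsor.

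What would be lost is the pregnancy itself and the scheduled enquiry into how it ended. Normal outcomes would not be counted, so any adverse outcome that did surface would have no denominator. The combination is new, and section 2.3.1 mentions irreversible effects on spermatogenesis in rats given MK-6482. Even a handful of fully documented pregnancies would therefore be useful safety information. The number is likely to be very small, and the matter does not touch sample size, power or the response-rate analyses.

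**Working it through.** No statistical figure is involved. The check compares the stated periods and then asks whether any other section closes the difference.

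**Inputs**
- Reporting window R = 3 months after the last study drug, both arms (7.2.9).
- Contraception period C: "6 months after completion abemaciclib plus MK-6482 and at least 3 weeks after the completion of abemaciclib administration" (3.1.8). I take this as 6 months for arm 2 and a 3-week minimum for arm 1.

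**Step 1. Difference by arm, gap = C - R**

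| Arm | C | R | Gap |
|---|---|---|---|
| 1 (abemaciclib) | at least 3 weeks | 3 months | none; R is longer than the stated minimum C |
| 2 (combination) | 6 months | 3 months | 6 - 3 = 3 months |

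For arm 2 the uncovered part is 3/6 = 50% of the post-treatment contraception period. That is a share of calendar time, not of events or of risk.

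**Step 2. Effect of the starting point.** Section 7.2.9 counts from the last study drug; 3.1.8 counts from the end of the combination. Several tables in section 6 stop MK-6482 while abemaciclib continues. If the combination ended d months before the last abemaciclib dose, and the 6 months run from the end of the combination, the gap is (6 - d) - 3 = 3 - d months, and nil once d reaches 3. So 3 months is the maximum, reached when both drugs stop together.

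**Step 3. Do other windows close it?**
- Active safety follow-up (5.7): 90 days or less. It ends at about the same point as R.
- SAE reporting to Merck regardless of relatedness (7.3.4): 90 days or less.
- AE reporting to the Overall PI (7.3.1): 30 days.
- Survival contact (5.7): every 6 months, so a contact is planned around the end of the contraception period, but its stated content is survival and next treatment, not pregnancy.

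None of these makes a pregnancy starting in months 3 to 6 reportable.

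**Step 4. What remains reportable in months 3 to 6?**

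| Event in arm 2 | Reportable? | Depends on |
|---|---|---|
| Abortion of any kind | Yes (7.2.9) | site learning of it |
| Birth defect, exposed female subject's child | Yes (7.2.9) | site learning of it |
| SAE attributed to study drug | Yes (7.2.10, 7.3.4) | attribution and awareness |
| Anomaly or cancer in later-conceived offspring of a female patient | Yes (7.2.10) | awareness |
| Ongoing or uneventful pregnancy | Not as such | reading of *on study* |
| Enquiry into outcome | Not clearly mandated | reading of *on study* |

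**Step 5. Two readings of *on study* in 7.2.9**
- On treatment: the 3-month limit operates, and the arm 2 gap is up to 3 months.
- Until a section 5.8 criterion applies: a woman in survival follow-up is still on study, her pregnancy is reportable, and there is no gap. The 3-month limit then has almost nothing to do, since few participants leave the study under 5.8 with 3 months of contactable follow-up to come. The opening sentence of 7.2.9 also pairs *on study* with stopping treatment, which points to the first reading.

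**A related point.** Section 3.1.8 applies the 6 months to men as well, but the birth-defect sentence in 7.2.9 and the offspring sentence in 7.2.10 name only female patients. Coverage of partner pregnancies is therefore not express.

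**The case against.** The strongest reply has four parts.

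1. **There may be no gap.** Section 5.8 defines going off study narrowly and 5.7 keeps participants in contact for up to 2 years, so a woman in months 3 to 6 is arguably still on study. This reading is available, which is why the conclusion is conditional. It does not settle the matter, because it leaves the 3-month limit almost redundant and fits poorly with the opening sentence of 7.2.9.

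2. **Bad outcomes are covered.** This stands. A reader might infer from the mismatch that arm 2 pregnancies in months 3 to 6, and their outcomes, simply go unreported. The documents do not support that: 7.2.9, 7.2.10 and 7.3.4 keep the adverse outcomes reportable with no end date. The fetal-outcome sentence in 3.1.8 also carries no 3-month limit, although it follows a sentence about pregnancy during participation, so its reach is uncertain. These provisions wait for someone to learn of an event or attribute it. They do not bring in the pregnancy itself or its normal outcome.

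3. **The two periods serve different purposes.** A reader might treat the 6 months as the protocol's declared period of fetal risk. It is not stated as such; it is a contraception undertaking within the eligibility criteria. The 3 months also fits the 90-day safety structure elsewhere. That explains where the figure may come from, but not why reporting should stop while contraception is still required.

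4. **The yield is tiny.** Arm 2 plans 23 to 26 patients, and the number of women of child-bearing potential is not given. This is right, and it fixes the priority as low.

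**Conclusion.** The concern holds in a limited form. For arm 2, the pregnancy reporting window is up to 3 months shorter than the contraception period. Unless *on study* extends through survival follow-up, a pregnancy starting in months 3 to 6 is not reportable as such and has no mandated outcome follow-up. Arm 1 is unaffected.

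The conclusion rests on three assumptions: the 6 months belongs to arm 2 and the 3 weeks to arm 1; both drugs stop together (otherwise the gap is smaller); and *on study* means on treatment.

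The loss is confined to ongoing and uneventful pregnancies, and to adverse outcomes that never reach the investigator or are not attributed. Expected events are few and the documents allow no estimate of their number. No efficacy endpoint or analysis changes. This is a minor inconsistency worth correcting. The documents do not show which of the two durations is appropriate, and this point takes no position on that.

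**What to change.** Reconcile 7.2.9 with 3.1.8 so that pregnancy reporting and outcome follow-up cover the post-treatment contraception period that the protocol sets for each arm, whatever duration the sponsor settles on. Count both periods from the same date. State whether *on study* in 7.2.9 means on treatment or until a section 5.8 criterion applies. It would help to say in the same edit whether partner pregnancies are included.

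The cost is a few words in 7.2.9 and possibly a few extra reports. No visit is added: the 6-monthly contact by phone and record review in 5.7 is already planned and could carry the question.

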7.2.10 Post-Study Adverse Events

The investigator should expeditiously report any SAE occurring after a patient has completed or discontinued study participation if attributed to prior study drugs exposure. If the investigator should become aware of the development of cancer or a congenital anomaly in a subsequently conceived offspring of a female patient who participated in the study, this should be reported as an SAE.

7.3 Adverse Event Reporting

7.3.1 Reporting to DFCI

Investigators must report to the Overall PI any adverse event that occurs after the initial dose of study treatment, during treatment, or within 30 days of the last dose of treatment on the local institutional SAE form.

In the event of an unanticipated problem or life-threatening complications **treating investigators** must immediately notify the Overall PI.

SAEs, whether related or unrelated to the study drugs, should be transmitted to the sponsor within 24 hours of the awareness date.

7.3.2 For Multi-Center Trials where a DF/HCC investigator is serving as the Sponsor, each external site must abide by the reporting requirements set by the DF/HCC. This applies to any medical event equivalent to an unexpected grade 2 or 3 with a possible, probable or definite attribution, unexpected grade 4 toxicities, and grade 5 (death) regardless of study phase or attribution.

DF/HCC Adverse Event Reporting Guidelines are as follows:

- Investigative sites within DF/HCC will report AEs directly to the DFCI Office for Human Research Studies (OHSR) per the DFCI IRB reporting policy.
- Other investigative sites will report AEs to their respective IRB according to the local IRB's policies and procedures in reporting adverse events. A copy of the submitted institutional AE form should be forwarded to the Overall PI within the timeframes detailed in the **Table 14**.

Table 14. Guidelines for adverse events reporting.

Attribution	DF/HCC Reportable Adverse Events(AEs)				
	Gr. 2 & 3 AE Expected	Gr. 2 & 3 AE Unexpected	Gr. 4 AE Expected	Gr. 4 AE Unexpected	Gr. 5 AE Expected or Unexpected
Unrelated Unlikely	Not required	Not required	10 calendar days [#]	10 calendar days	24 hours*
Possible Probable Definite	Not required	10 calendar days	10 calendar days [#]	10 calendar days	24 hours*
# If listed in protocol as expected and not requiring expedited reporting, event does not need to be reported.					
* For participants enrolled and actively participating in the study or for AEs occurring within 30 days of the last intervention, the AE should be reported within 1 business day of learning of the event.					

- The Overall PI will submit AE reports from outside institutions to the DFCI OHRS according to DFCI IRB policies and procedures in reporting adverse events.

